5.3 Radiotherapy

Radiotherapy will be performed using external beam ionizing radiation or by brachytherapy as standard therapy in accordance with institutional standard practice.

5.4 Pembrolizumab

Pembrolizumab will be provided by Merck. Pembrolizumab will be prepared and administered as per MSKCC guidelines. Please refer to investigator brochure for additional information

The investigator shall take responsibility for and shall take all steps to maintain appropriate records and ensure appropriate supply, storage, handling, distribution and usage of investigational product in accordance with the protocol and any applicable laws and regulations. Clinical supplies will be affixed with a clinical label in accordance with regulatory requirements.

6.0 CRITERIA FOR SUBJECT ELIGIBILITY

6.1 Subject Inclusion Criteria

- 1. Be willing and able to provide written informed consent/assent for the trial.
- 2. Histologically- or cytologically- confirmed CRC.
- 3. Metastatic or recurrent CRC.

- 4. Subjects have received two or more standard available therapies known to prolong survival and for which they would be considered eligible. Such therapies should include regimens containing oxaliplatin and irinotecan in combination with a fluoropyrimidine if appropriate (e.g., FOLFOX and FOLFIRI or their variants).
- 5. At least one tumor for which palliative RT is considered appropriate standard therapy (cohort 1); or, at least one tumor for which palliative ablation is considered appropriate standard therapy (cohort 2).
- 6. At least one index lesion that will not undergo RT or ablation, and which is measurable based on RECIST 1.1.
- 7. Be ≥ 18 years of age on day of signing informed consent.
- 8. Consent for tumor biopsies and blood draws for research purposes.
- 9. Consent for use of available archived tissue for research purposes.
- 10. Have a performance status of 0 or 1 on the ECOG Performance Scale.
- 11. Demonstrate adequate organ function as defined in Table 6.1, all screening labs should be performed within 6 weeks of treatment initiation.

Table 6.1 Adequate Organ Function Laboratory Values

0	II -h
System	Laboratory Value
Hematological	
Absolute neutrophil count (ANC)	≥1,500 /mcL
Platelets	≥100,000 / mcL
Renal	
Serum creatinine	≤1.5 X upper limit of normal (ULN)
OR	OR
Measured or calculated ^a creatinine	
clearance (GFR can also be used in	≥60 mL/min for subject with creatinine levels > 1.5 X
place of creatinine or CrCl)	institutional ULN
Hepatic	
Serum total bilirubin	≤ 1.5 XULN OR
	Direct bilirubin ≤ ULN for subjects with total bilirubin levels >
	1.5 ULN
AST (SGOT) and ALT (SGPT)	≤ 2.5 XULN OR
AST (SGOT) and ALT (SGPT)	≤ 5 X ULN for subjects with liver metastases
Coagulation	
International Normalized Ratio (INR) or	≤1.5 X ULN unless subject is receiving anticoagulant therapy
` '	as long as PT or PTT is within therapeutic range of intended
Prothrombin Time (PT)	use of anticoagulants
Activated Partial Thromboplastin Time	≤1.5 X ULN unless subject is receiving anticoagulant the rapy
•	as long as PT or PTT is within therapeutic range of intended
(aPTT)	use of anticoagulants
^a Creatinine clearance should be calcula	ted per institutional standard.

- 12. Female subject of childbearing potential should have a negative serum pregnancy within 2 weeks prior to starting radiation therapy or undergoing ablation.
- 13. Female subjects of childbearing potential should be willing to use 2 methods of birth control or be surgically sterile, or abstain from heterosexual activity for the course of the study through 120 days after the last dose of study medication (Reference Section 9.5.2). Subjects of childbearing potential are those who have not been surgically sterilized or have not been free from menses for > 1 year.
- 14. Male subjects should agree to use an adequate method of contraception starting with the first dose of study therapy through 120 days after the last dose of study therapy.

6.2 Subject Exclusion Criteria

- 1. Is currently participating in or has participated in a study of an investigational agent or using an investigational device within 4 weeks of the first dose of treatment.
- 2. Has a diagnosis of immunodeficiency or is receiving systemic steroid therapy or any other form of immunosuppressive therapy within 7 days prior to the first dose of trial treatment.
- 3. Has had a prior monoclonal antibody within 4 weeks prior to study Day 1 or who has not recovered (i.e., ≤ Grade 1 or at baseline) from adverse events due to agents administered more than 4 weeks earlier.
- 4. Has had prior chemotherapy, targeted small molecule therapy within 2 weeks prior to study Day 1 or who has not recovered (i.e., ≤ Grade 1 or at baseline) from adverse events due to a previously administered agent.
 - Note: Subjects with ≤ Grade 2 neuropathy are an exception to this criterion and may qualify for the study.
- 5. If subject received major surgery, they must have recovered adequately from the toxicity and/or complications from the intervention prior to starting therapy.
- 6. Has a known additional malignancy that is progressing or requires active treatment. Exceptions include basal cell carcinoma of the skin, squamous cell carcinoma of the skin, or in situ cervical cancer that has undergone potentially curative therapy.
- 7. Has known active central nervous system (CNS) metastases and/or carcinom atous meningitis. Subjects with previously treated brain metastases may participate provided they are stable (without evidence of progression by imaging for at least four weeks prior to the first dose of trial treatment and any neurologic symptoms have returned to baseline), have no evidence of new or enlarging brain metastases, and are not using steroids for at least 7 days prior to trial treatment.
- 8. Has an active autoimmune disease requiring systemic treatment within the past 3 months or a documented history of clinically severe autoimmune disease, or a syndrome that requires systemic steroids or immunosuppressive agents. Subjects with vitiligo or resolved childhood asthma/atopy would be an exception to this rule. Subjects that

require intermittent use of bronchodilators or local steroid injections would not be excluded from the study. Subjects with hypothyroidism stable on hormone replacement or Sjorgen's syndrome will not be excluded from the study.

- 9. Has evidence of interstitial lung disease or active, non-infectious pneumonitis.
- 10. Has an active infection requiring systemic therapy.
- 11. Has a history or current evidence of any condition, therapy, or laboratory abnormality that might confound the results of the trial, interfere with the subject s participation for the full duration of the trial, or is not in the best interest of the subject to participate, in the opinion of the treating investigator.
- 12. Has known psychiatric or substance abuse disorders that would interfere with cooperation with the requirements of the trial.
- 13. Is pregnant or breastfeeding, or expecting to conceive or father children within the projected duration of the trial, starting with the pre-screening or screening visit through 120 days after the last dose of trial treatment.
- 14. Has received prior therapy with an anti-PD-1, anti-PD-L1, anti-PD-L2, anti-CD137, or anti-Cytotoxic T-lymphocyte-associated antigen-4 (CTLA-4) antibody (including ipilimumab or any other antibody or drug specifically targeting T-cell co-stimulation or checkpoint pathways).
- 15. Has a known history of Human Immunodeficiency Virus (HIV) (HIV 1/2 antibodies).
- 16. Has known active Hepatitis B (e.g., HBsAg reactive) or Hepatitis C (e.g., HCV RNA [qualitative] is detected).
- 17. Has received a live vaccine within 30 days prior to the first dose of trial treatment.

7.0 RECRUITMENT PLAN

This study will be available to all patients seen at Memorial Hospital, who meet the eligibility criteria outlined in section 6.0.

Memorial Hospital is a referral center for CRC. In addition, the study may be placed on the institutional Website to maximize patient recruitment. Patients will be identified from medical oncology clinics for treatment of their disease.

The investigators take due notice of the NIH policy concerning inclusion of women and minorities in clinical research populations. There will be no limitation to access with regard to race or gender. Patients will be required to read, agree to, and sign an IRB-approved informed consent form prior to registration on this trial. The registration procedure will be conducted as described in section 15.0. Patients will not receive payment for their participation on this study.

8.0 PRETREATMENT EVALUATION

To be completed prior to starting RT or ablation and within 6 weeks of starting pembrolizumab:

- CT scan with contrast (chest, abdomen and pelvis). If patient is unable to receive CT contrast, or the abdominal/pelvic target lesion is indeterminate on CT scan then MRI with contrast (abdomen and pelvis) plus CT chest without contrast may be perfromed. Noncontrast CT CAP may be used if the target lesion(s) do not require contrast for accurate measurements.
- 12-lead Electrocardiogram (EKG).
- Signed informed consent for study participation.
- History and physical examination, including height, weight, vital signs (temperature, pulse rate, respiration rate, blood pressure), and performance status (ECOG).
- Serum pregnancy test for all women of childbearing potential (within two weeks of starting RT or ablation). If the test result is positive related to pregnancy, the patient will not be allowed to participate in this study.
- CBC with differential and platelet count, serum chemistries (Na, Cl, BUN, Creatinine, K, CO2, and glucose), LFTs (AST, ALT, alkaline phosphatase, total bilirubin), calcium, albumin, total protein, and CEA
- Serology for HepBsAg, HepBcAb and hepatitis C antibody (negative test acceptable prior to screening period)
- Blood test for research purposes.
- Perform baseline tumor biopsy for research purposes at the time of fiducial placement or ablation or during a separate procedure.

9.0 TREATMENT/INTERVENTION PLAN

9.1 Dosing Instructions and Schedule

Drug	Dose/	Dose	Route of	Regimen/	Use
	Potency	Frequency	Administration	Treatment Period	
Pembrolizumab	200 mg	Q3W	IV infusion	n/a	Experimental

The first day of dosing is considered Day 1. Subjects will receive pembrolizumab as an IV infusion. Refer to "MK-3475 Drug Preparation Instructions" manual.

Trial treatment should be administered on Day 1 of each cycle. Trial treatment may be administered up to 3 days before or after the scheduled Day 1 of each cycle due to administrative reasons. All trial treatments will be administered on an outpatient basis.

Pembrolizumab will be administered as a 30 minute IV infusion (every effort should be made to target infusion timing to be as close to 30 minutes as possible. However, given the variability of infusion pumps from site to site, a window of -5 minutes and +10 minutes is permitted (i.e., infusion time is 30 minutes: -5 min/+10 min).

9.2 Monitoring of Dose Administration

Subjects will be monitored during and after infusion with assessment of vital signs per institutional practice.

In the event of an infusion-related reaction, refer to See appendix C for guidance.

As with any antibody, allergic reactions to dose administration are possible. Appropriate drugs and medical equipment to treat acute anaphylactic reactions must be immediately available, and study personnel must be trained to recognize and treat anaphylaxis. The study site must have immediate access to emergency resuscitation teams and equipment in addition to the ability to admit subjects to an intensive care unit if necessary.

9.3 Concomitant Medications

9.3.1 Permitted Concomitant Medication

Investigators may prescribe concomitant medications or treatments (e.g., acetaminophen, diphenhydramine) deemed necessary to provide adequate prophylactic or supportive care except for those medications identified as "excluded" as listed in Section 9.3.2.

9.3.2 Excluded Concomitant Medications

Subjects must be instructed not to take any medications, including over-the-counter products, without first consulting with the investigator.

The following medications are considered exclusionary during the study. The Principal Investigator must be notified if a subject receives any of these during the study.

- Any investigational anticancer therapy.
- Any concurrent chemotherapy (except as permitted above), immunotherapy, or biologic therapy. Concurrent use of hormones for non-cancer-related conditions (e.g., insulin for diabetes and hormone replacement therapy) is acceptable.
- Immunosuppressive medications including, but not limited to systemic corticosteroids (>10 mg/day prednisone or equivalent), methotrexate, azathioprine, and tumor necrosis factor alpha (TNF-α) blockers. Use of immunosuppressive medications for the management of investigational product-related AEs, in subjects with contrast allergies is acceptable. In addition, use of inhaled and intranasal corticosteroids is permitted.

9.4 Dose Modification

Refer to APPENDIX C for guidance in the event of a drug-related adverse event. Pembrolizumab dosing may continue in the event of an unrelated, grade 1 or tolerable grade 2 adverse event.

Subjects who experience a recurrence of the same severe or life-threatening event at the same grade or greater with re-challenge of pembrolizumab should be discontinued from trial treatment.

9.4.1 Supportive Care Guidelines

- Nausea/vomiting: Nausea and vomiting should be treated aggressively, and consideration should be given in subsequent cycles to the administration of prophylactic antiemetic therapy according to standard institutional practice. Subjects should be strongly encouraged to maintain liberal oral fluid intake.
- Anti-infectives: Subjects with a documented infectious complication should receive oral
 or IV antibiotics or other anti-infective agents as considered appropriate by the treating
 investigator for a given infectious condition, according to standard institutional practice.

9.5 Diet/Activity/Other Considerations

9.5.1 Diet

Subjects should maintain a normal diet unless modifications are required to manage an AE such as diarrhea, nausea or vomiting.

9.5.2 Contraception

Pembrolizumab may have adverse effects on a fetus in utero. Furthermore, it is not known if pembrolizumab has transient adverse effects on the composition of sperm. Non-pregnant, non-breast-feeding women may be enrolled if they are willing to use 2 methods of birth control or are considered highly unlikely to conceive. Highly unlikely to conceive is defined as 1) surgically sterilized, or 2) postmenopausal (a woman who is ≥45 years of age and has not had menses for greater than 1 year will be considered postmenopausal), or 3) not heterosexually active for the duration of the study. The two birth control methods can be either two barrier methods or a barrier method plus a hormonal method to prevent pregnancy. Subjects should start using birth control from study Visit 1 throughout the study period up to 120 days after the last dose of study therapy.

The following are considered adequate barrier methods of contraception: diaphragm, condom (by the partner), copper intrauterine device, sponge, or spermicide. Appropriate hormonal contraceptives will include any registered and marketed contraceptive agent that contains an estrogen and/or a progestational agent (including oral, subcutaneous, intrauterine, or intramuscular agents).

Subjects should be informed that taking the study medication may involve unknown risks to the fetus (unborn baby) if pregnancy were to occur during the study. In order to participate in the study they must adhere to the contraception requirement (described above) for the duration of

the study and during the follow-up period defined in section 11.1.2 - Pregnancies. If there is any question that a subject will not reliably comply with the requirements for contraception, that subject should not be entered into the study.

9.5.3 Use in Pregnancy

If a subject inadvertently becomes pregnant while on treatment with pembrolizumab, the subject will immediately be removed from the study. The site will contact the subject at least monthly and document the subject"s status until the pregnancy has been completed or terminated. The outcome of the pregnancy will be reported to Merck without delay and within 24 hours if the outcome is a serious adverse experience (e.g., death, abortion, congenital anomaly, or other disabling or life-threatening complication to the mother or newborn). The study investigator will make every effort to obtain permission to follow the outcome of the pregnancy and report the condition of the fetus or newborn to Merck. If a male subject impregnates his female partner the study personnel at the site must be informed immediately and the pregnancy reported to Merck and followed as described above and in Section 11.1.2.

9.5.4 Use in Nursing Women

It is unknown whether pembrolizumab is excreted in human milk. Since many drugs are excreted in human milk, and because of the potential for serious adverse reactions in the nursing infant, subjects who are breast-feeding are not eligible for enrollment.

9.6 Subject Withdrawal/Discontinuation Criteria

Subjects may withdraw consent at any time for any reason or be dropped from the trial at the discretion of the investigator should any untoward effect occur. In addition, a subject may be withdrawn by the investigator or the Sponsor if enrollment into the trial is inappropriate, the trial plan is violated, or for administrative and/or other safety reasons.

A subject must be discontinued from the trial for any of the following reasons:

- The subject or legal representative (such as a parent or legal guardian) withdraws consent.
- Confirmed radiographic disease progression

Note: A subject may be granted an exception to continue on treatment with confirmed radiographic progression if clinically stable or clinically improved.

- Unacceptable adverse experiences
- Intercurrent illness that prevents further administration of treatment
- Investigator"s decision to withdraw the subject
- The subject has a confirmed positive serum pregnancy test
- Noncompliance with trial treatment or procedure requirements
- The subject is lost to follow-up

• Completed 24 months of treatment with pembrolizumab

Note: 24 months of study medication is calculated from the date of first dose. Subjects who stop pembrolizumab after 24 months may be eligible for up to one year of additional study treatment at the discretion of the PI if they responded during the initial 24 months and then progressed after stopping study treatment.

Administrative reasons

After the end of treatment, each subject will be followed for 30 days for adverse event monitoring (serious adverse events will be collected for 90 days after the end of treatment). Subjects who discontinue for reasons other than progressive disease will have post-treatment follow-up for disease status until disease progression, initiating a non-study cancer treatment, withdrawing consent or becoming lost to follow-up, for up to 2 years. After documented disease progression each subject will be followed by telephone (if not otherwise following up at Memorial Hospital) for overall survival until death, withdrawal of consent, the end of the study, or 2 years, whichever occurs first.

9.7 Clinical Criteria for Early Trial Termination

Early trial termination will be the result of the criteria specified below:

- 1. Quality or quantity of data recording is inaccurate or incomplete
- 2. Poor adherence to protocol and regulatory requirements
- 3. Incidence or severity of adverse drug reaction in this or other studies indicates a potential health hazard to subjects
- 4. Plans to modify or discontinue the development of the study drug

In the event of Merck decision to no longer supply study drug, ample notification will be provided so that appropriate adjustments to subject treatment can be made.

9.8 RESEARCH BLOOD AND BIOPSY SPECIMENS

9.8.1 Research blood

For all patients, blood specimens will be obtained for research purposes during screening or on day 1, then at weeks 3, 6 and 9 (± 3 days). Additional blood draws beyond week 9 are permitted based upon interesting clinic/immunological findings.

Specimens should be collected prior to drug administration. Four (4) tubes of blood are to be collected in BD Vacutainer® CPT™ Cell Preparation Tubes with Sodium Heparin. Each tube should contain approximately 10 cc of blood. Peripheral blood mononuclear cells and plasma will then be isolated per institutional practice in the Immune Monitoring Facility (IMF).

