4.2 Intervention

Patients will be stratified according to eligibility for RT (cohort 1) or ablation (cohort 2). Patients in **cohort 1** will have at least one locally advanced or metastatic lesion for which palliative RT is considered appropriate standard therapy, and at least one other measurable index lesion that will not undergo RT. Patients in cohort 2 will have at least one metastatic lesion for which palliative ablation is considered appropriate standard therapy, and at least one other measurable index lesion that will not undergo ablation. Subjects in cohort 2 will undergo ablation of one or more lesions. The ablation method is at the discretion of the interventional radiologist. All subjects will undergo ablation or begin RT within 7 days prior to starting pembrolizumab. Pembrolizumab dosing may continue during RT. Subjects will receive pembrolizumab via IV infusion at 200 mg every three weeks (Q3W), and continue treatment Q3W until progression of disease, initiation of alternative cancer therapy, unacceptable toxicity, or other reasons to discontinue treatment occur, up to 24 months. Patients who had a prior response without another reason to discontinue therapy after 24 months will continue clinic visits, routine blood work (CBC, COMP, CEA) and CT/MRI every 9 weeks, and may resume treatment for an additional 12 months upon disease progression. Repeat palliative RT in cohort 1, or ablation in cohort 2, will be permitted in select cases for the treatment of isolated, non-target lesions. Patients will be evaluated by physical exam and routine blood tests every three weeks during the study period. CT or MRI will be performed during screening, and then at 9 week intervals. Tumor measurements and determination of tumor responses will be performed according to RECIST 1.1.

Subjects may continue to receive pembrolizumab beyond radiographic disease progression in the absence of clinical deterioration, and after discussion with the Principal Investigator.

All subjects will be followed up to 2 years for survival or until the study closes. Exploratory research studies to evaluate the effect of this therapy will be performed in patients using

research blood draws, and tumor biopsy at baseline, 1 week after completing RT or undergoing ablation (from the radiated/ablated lesion), and then 4 weeks after dose #1 of pembrolizumab (from a non-radiated/ablated lesion), for research purposes.

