- 11. Blood draws for research purposes performed during screening or day 1, then weeks 3, 6 and 9 for all patients. Additional blood draws beyond week 9 are permitted based upon interesting clinic/immunological findings for all patients.

- 12. Up to 20 x 5µm slides (unstained) of archived tissue will be requested on all patients for research purposes. For patients undergoing routine procedures during the study, additional tissue (up to 20 x 5µm slides (unstained)) may be obtained from each routine procedure. for research purposes.
- 13. Research tumor biopsy will be performed during fiducal placement or ablation or during a separate procedure, then 1 week (±3 days) after completing RT or ablation (from the radiated/ablated lesion) and 4 weeks after dose #1 of pembrolizumab (±1 week) from a non-ablated/radiated lesion. For patients that are unable to have biopsy 4 weeks after dose #1 of pembrolizumab, the procedure may be delayed up until Week 9.
- 14. RT begins or ablation is performed during cycle 1, within one week prior to dose 1 of Pembrolizumab.
- 15. EOS visit occurs 4(±1 wk) weeks after last dose of pembrolizumab. CT scan or MRI to be done only if last imaging was conducted greater than four weeks prior to the date of the Final Visit.

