The pharmacodynamic effect of pembrolizumab and RT or ablation on markers in peripheral blood, such as ICOS, HLA-DR, PD-1, CTLA-4; and, serum proteins, such as CXCL9; CXCL10, will be assessed by summary statistics, and investigated graphically to explore patterns of change over time, i.e.: pretreatment, then week 3, and week 9.

In addition, the relationship of TIL changes and tumor marker expression with measures of peripheral blood markers will be summarized descriptively.

Associations between the markers and response by RECIST will be explored.

Fisher's exact test will be employed to assess associations between categorical variables while Spearman's rank correlation will be used for continuous variables. Wilcoxon signed rank test will be used to test for differences in continuous expression tumor markers between pre- and post-treatment specimens while McNemar's test will be used to assess these relationships for binary markers. Fisher's exact test will be employed to assess associations between categorical variables.

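### The baseline research blood may be drawn on day 1, after ablation or the start of RT; this conflicts with Section 8 and dilutes the RT/ablation part of the exploratory blood-marker change

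*Combined protocol and SAP*

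**What the plan says.** Four places bear on when the baseline research blood is taken.

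- Section 8.0 (Pretreatment Evaluation) opens its list with "To be completed prior to starting RT or ablation and within 6 weeks of starting pembrolizumab". The research blood test is on that list.
- Section 9.8.1 (Research blood) gives a wider choice: "blood specimens will be obtained for research purposes during screening or on day 1, then at weeks 3, 6 and 9". Its only other timing condition is "Specimens should be collected prior to drug administration".
- Note 11 to the Study Calendar in Section 10.0 repeats the wider choice: "Blood draws for research purposes performed during screening or day 1, then weeks 3, 6 and 9 for all patients". The calendar row itself marks the baseline blood under Screening only, with no mark at week 0.
- Section 14.0 (Biomarker Analysis) sets out to describe what pembrolizumab together with RT or ablation does to peripheral blood markers, as "patterns of change over time, i.e.: pretreatment, then week 3, and week 9". It does not say before which treatment the pretreatment sample must fall.

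Three further statements fix the timeline. Section 9.1 says "The first day of dosing is considered Day 1". Section 4.2 says "All subjects will undergo ablation or begin RT within 7 days prior to starting pembrolizumab", and adds that pembrolizumab may be given while RT is still under way. Calendar note 14 agrees on the interval: "RT begins or ablation is performed during cycle 1, within one week prior to dose 1 of Pembrolizumab".

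**The concern.** A sample taken on day 1 precedes pembrolizumab but normally follows ablation or the first RT fraction. It satisfies Section 9.8.1 and breaches Section 8. The pre-dose condition in 9.8.1 protects the baseline from the drug, not from the local treatment.

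This matters because the local treatment is part of what the blood analysis is meant to describe. The rationale in Section 3.3 is that destroying a tumor releases antigen and starts a T-cell response, which PD-1 blockade then strengthens. Section 9.8.3.1 would read on-treatment rises in antigen-specific T cells as evidence of adaptive immunity. Any rise already present on day 1 would be counted as baseline and subtracted.

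Section 14 also relates changes in tumor-infiltrating lymphocytes to blood markers. Section 8 puts the baseline biopsy before RT or ablation, so in a patient with a day 1 blood draw the two baselines would sit on opposite sides of the local treatment. A blood sample not taken before RT or ablation cannot be obtained later, and with 9 to 24 patients per cohort there is little room for a mixed baseline.

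A smaller mismatch sits in the same Section 14 sentence: blood is collected at weeks 3, 6 and 9, but the analysis names only weeks 3 and 9.

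**Working it through.** The plan states no figure on this point, so there is none to reproduce. The check compares the texts, then illustrates the size of the effect.

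**Step 1: where a day 1 draw falls.** Let T be the days from ablation, or from the start of RT, to the first pembrolizumab dose. Section 4.2 and calendar note 14 give 0 ≤ T ≤ 7. By Section 9.1 that dose is day 1, so a day 1 draw comes T days after the local treatment was done or begun. Only if T = 0, and the blood is taken before the procedure that same day, can a day 1 draw also meet Section 8.

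**Step 2: whether the word screening protects the baseline.** Calendar note 2 defines the screening window by the 6 weeks before dose 1, not by RT or ablation. The calendar marks RT and ablation in the Screening column too. A draw made during screening could therefore still follow RT or ablation. Only Section 8 ties the blood to the local treatment.

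**Step 3: dilution of the change from baseline.** Notation, with f and e both assumptions because the documents give neither:

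- D: mean contribution of RT or ablation to a marker at a later visit.
- e: share of D already present on day 1.
- f: share of patients whose baseline is the day 1 draw.

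A patient drawn before RT or ablation shows D in the change from baseline. A patient drawn on day 1 shows D − eD. The average is

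(1 − f) × D + f × (1 − e) × D = D × (1 − f × e),

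so the share of the RT/ablation component kept is 1 − f × e.

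| f | e | 1 − f × e | Share kept |
|---|---|---|---|
| 0 | any | 1 | 100% |
| 0.25 | 0.25 | 1 − 0.0625 | 94% |
| 0.5 | 0.5 | 1 − 0.25 | 75% |
| 0.5 | 1 | 1 − 0.5 | 50% |
| 1 | 1 | 1 − 1 | 0% |

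In a full cohort of 24, f = 0.25 is 6 patients (0.25 × 24) and f = 0.5 is 12 (0.5 × 24). The formula takes the day 1 shift to be a fraction of the later one (e between 0 and 1) and D and e to be the same on average whichever day blood was drawn. An early shift that later reverses would distort the change in another way.

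**Step 4: week 6.** The summary in Section 1.0, Section 9.8.1, calendar note 11 and the Appendix A requisition all schedule blood at weeks 3, 6 and 9. Section 14 names two of these three on-treatment times and gives no reason for leaving out the third.

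**The case against.** The strongest reply is that day 1 is the exception. Section 8 and the calendar row both place the baseline draw at screening, and the documents do not say how many patients will be drawn on day 1. If f is small, the dilution is small. The analysis is also exploratory, uses summary statistics and graphs, and includes several assays that are only optional. All of this stands, and it limits the weight of the point. It does not resolve the conflict: staff who follow 9.8.1 or note 11 may draw on day 1, and Section 14 would then call the sample pretreatment.

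A reader might go further than the documents allow in three ways.

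- *That a day 1 baseline removes the RT/ablation effect.* That requires every patient to be drawn on day 1 and the whole effect to be present by then. Section 3.3 gives no time scale for the immune response, day 1 is at most 7 days after the procedure, and in cohort 1 RT need only have begun. Later effects stay in the change scores, and patients drawn before RT or ablation are unaffected.
- *That the cohorts can no longer be compared.* No such comparison is planned. There is no randomization, and Section 14 summarizes exploratory results by cohort.
- *That week 6 data are lost.* The samples are collected, and nothing bars their analysis. One descriptive list omits them.

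It may also be said that a day 1 sample is a sound reference for pembrolizumab alone. That is right, and the fix should keep it for that use.

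**Conclusion.** The inconsistency is real: Section 8 requires the baseline research blood before RT or ablation, while Section 9.8.1 and calendar note 11 also accept day 1, which is 0 to 7 days after ablation or the start of RT. For patients drawn on day 1, the pretreatment value in Section 14 absorbs whatever effect is already present, so the RT/ablation component of the mean change is diluted by f × e. The size cannot be fixed from the documents. Over the assumed values shown, the share kept runs from 94% to 50%, with 100% and 0% as the limits.

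The consequence stops at the exploratory blood-marker analyses and their link to the biopsy data. The primary endpoint is response by RECIST 1.1 and uses no blood marker, so the Simon rule and its error rates are unaffected. The correction is still worth making, because a missed sample cannot be replaced and the change is one of wording. The missing week 6 is a minor addition.

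**What to change.** 1. In Section 9.8.1 and calendar note 11, replace the choice between screening and day 1 with *during screening, before RT or ablation*, matching Section 8. Deleting the day 1 option alone is not enough, because the calendar's Screening column itself contains RT and ablation.
2. Label any sample drawn on day 1 *post-RT/ablation, pre-pembrolizumab*. Do not pool it with baselines taken before RT or ablation; it may serve as a pre-pembrolizumab reference.
3. In Section 14, list the blood time points as *pretreatment (before RT/ablation), week 3, week 6 and week 9*, matching the collection schedule.

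The cost is slightly less flexibility in scheduling one blood draw. Section 8 already asks for that draw before RT or ablation, so no visit is added.
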